9.1 Measurable Disease

Measurable lesions are defined as those that can be accurately measured in at least one dimension (longest diameter to be recorded) as > 20 mm with conventional techniques (CT, MRI, x-ray) or as > 10 mm with spiral CT scan. All tumor measurements must be recorded in millimeters (or decimal fractions of centimeters). To be considered pathologically enlarged and measurable, a lymph node must be ≥ 15 mm in short axis when assessed by CT scan.

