8.1.18 Diagnostic Imaging

Diagnostic imaging will be performed at screening, 3 months post EBRT, and 12 months post EBRT. Imaging studies can be obtained at any time if clinically indicated by the treating physician.

Imaging studies may consist of any combination of CT, MR, or PET-MR scans, as clinically indicated. If cross sectional imaging is unable to be obtained, other imaging modalities may be used (see section 9.3). The imaging study performed at screening should be repeated at subsequent assessments.

Imaging studies are standard clinical care procedures being done within routine care guidelines.

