9 CRITERIA FOR DISEASE ASSESSMENT

For the purposes of this study, subjects will be evaluated for evidence of response and progression at 3 and 12 months post-completion of the EBRT portion of the protocol – see study calendar. Only those subjects who receive a treatment dose of study drug will be assessed for response and/or progression. Those with inadequate uptake after the dosimetry test dose will only be followed for safety measures.

Response and progression will be evaluated in two distinct fashions. For those without evidence of metastatic disease at the time of study enrollment, response and progression will be evaluated using the new international criteria proposed by the Response Evaluation Criteria in Solid Tumors (RECIST) 1.1 Committee (Eisenhauer *et al.*, 2009).

For those with metastatic disease at the time of study enrollment, study lesions will be defined within the locoregional recurrence field that will be receiving EBRT. Those lesions will be assessed for response and progression using RECIST 1.1 criteria. Lesions outside of the radiation field can be assessed for response to CLR 131 alone. Once palliative systemic therapy is initiated for systemic disease burden, subjects will be censored as having disease progression, regardless of the status of the locoregional target lesions.

Note: Lesions are either measurable or non-measurable using the criteria provided below.

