9.2 Non-measurable Disease

All other lesions (or sites of disease), including small lesions (longest diameter < 20 mm with conventional techniques or < 10 mm using spiral CT scan or pathological lymph nodes with ≥ 10 to < 15 mm short axis), are considered non-measurable disease. Bone lesions, leptomeningeal disease, ascites, pleural/pericardial effusions, lymphangitis cutis/pulmonis, inflammatory breast disease, abdominal masses (not followed by CT or MRI), and cystic lesions are all non-measurable.

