9.3 Guidelines for Evaluation of Measurable Disease

Measurements will be recorded for the study from standard of care scans in the medical records maintained as part of standard clinical care. All measurements should be taken and recorded in metric notation using a ruler or calipers. All baseline evaluations should be performed as closely as possible to the beginning of treatment and never more than 4 weeks before the beginning of the treatment.

Note: Tumor lesions that are situated in a previously irradiated area can be considered measurable only if there is documented growth of the lesion, and at least 8 weeks have elapsed since completion of radiation treatments.

When possible, the same method of assessment and the same technique should be used to characterize each identified and reported lesion at baseline and during follow-up. Imaging-based evaluation is preferred to evaluation by clinical examination when both methods have been used to assess the antitumor effect of a treatment.

Clinical lesions: Clinical lesions will only be considered measurable when they are superficial and ≥ 10 mm diameter (e.g., skin nodules and palpable lymph nodes). In the case of skin lesions, documentation by color photography, including a ruler to estimate the size of the lesion, is recommended.

Chest x-ray: Lesions on chest x-ray are acceptable as measurable lesions when they are clearly defined and surrounded by aerated lung. However, CT is preferable.

Conventional CT and MRI: These techniques should be performed with cuts of 10 mm or less in slice thickness contiguously. Spiral CT should be performed using a 5 mm contiguous reconstruction algorithm. This applies to tumors of the chest, abdomen, and pelvis. Head and neck tumors and those of extremities usually require specific protocols.

Ultrasound: When the primary endpoint of the study is objective response evaluation, US should not be used to measure tumor lesions. It is, however, a possible alternative to clinical measurements of superficial palpable lymph nodes, subcutaneous lesions, and thyroid nodules. Ultrasound might also be useful to confirm the complete disappearance of superficial lesions usually assessed by clinical examination.

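### Whether a non-nodal lesion of more than 10 and up to 20 mm counts as measurable depends on the scanner, and modality may differ between subjects, so ORR can depend on it too

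*Combined protocol and SAP*

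**What the plan says.** Section 9 adopts RECIST 1.1 for response and progression. For subjects with metastatic disease it says of the lesions in the radiation field: "Those lesions will be assessed for response and progression using RECIST 1.1 criteria". It then directs that lesions be classed by the protocol's own criteria that follow.

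- **Section 9.1** sets the measurable limit at "> 20 mm with conventional techniques (CT, MRI, x-ray) or as > 10 mm with spiral CT scan". For nodes it adds that "a lymph node must be ≥ 15 mm in short axis when assessed by CT scan".
- **Section 9.2** puts everything else in the non-measurable class, including lesions with "longest diameter < 20 mm with conventional techniques or < 10 mm using spiral CT scan" and nodes of 10 to under 15 mm short axis.
- **Section 9.3** has a separate rule for physical examination: "Clinical lesions will only be considered measurable when they are superficial and ≥ 10 mm diameter". Palpable lymph nodes are one of its examples.
- **Section 8.1.18** leaves modality open: "Imaging studies may consist of any combination of CT, MR, or PET-MR scans, as clinically indicated". It also says: "The imaging study performed at screening should be repeated at subsequent assessments".

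Inclusion criterion 6 (section 5.2) accepts an evaluable lesion whether measurable or not. Section 5.5.1 defines efficacy evaluability by complete CLR 131 dosing and at least one post-infusion assessment, and does not mention measurable disease. ORR (section 3.2.2) counts partial and complete responses. Section 14.3.2 reports it as a proportion with an exact interval.

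**The concern.** Tumour size and treatment effect should decide whether a subject can be scored a partial response. Here a third factor enters: the type of scan chosen at baseline for clinical reasons, such as the site of the recurrence. Two subjects with the same lesion and the same shrinkage can be classed differently, one with a measured percentage change and one without. The endpoint at stake is ORR, the trial's only summary of tumour response, in at most 12 subjects at the MTD. With so few, reclassifying one or two subjects visibly changes the reported proportion.

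**Working it through.** The plan gives no ORR target, power or sample-size figure that depends on measurability, so there is no figure to reproduce. The check applies the protocol's limits to a range of lesion sizes and then follows the result through to ORR.

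**1. Classification of a non-nodal lesion by longest diameter (sections 9.1 to 9.3)**

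| Diameter | MRI or conventional CT (>20 mm) | Spiral CT (>10 mm) | Clinical, superficial only (≥10 mm) |
|---|---|---|---|
| 8 mm | no | no | no |
| 10 mm | no | no | yes |
| 11 mm | no | yes | yes |
| 15 mm | no | yes | yes |
| 20 mm | no | yes | yes |
| 21 mm | yes | yes | yes |

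The scanner-dependent band is above 10 mm and up to 20 mm. Section 9.1 does not name PET-MR; I read it as falling under MRI. The inequality signs of 9.1 (above 20, above 10) and 9.2 (below 20, below 10) do not meet at exactly 20 and 10 mm. Those sizes are non-measurable only through the catch-all opening of 9.2.

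**2. Basis for the split**

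Section 9.3 gives cuts of 10 mm or less for conventional CT and MRI, and a 5 mm reconstruction for spiral CT. The two limits are twice these figures: 2 × 10 = 20 mm and 2 × 5 = 10 mm. The same paragraph confines those settings to chest, abdomen and pelvis and says head and neck tumours usually need their own protocols. None is given.

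**3. Effect on one subject**

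A lesion shrinking from 15 to 10 mm changes by (15 − 10)/15 = 33.3%. On spiral CT this is a measured change in a measurable lesion. On MRI the lesion is non-measurable, and the protocol states no way to score a partial response in it.

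**4. Effect on ORR**

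One subject in 12 is 1/12 = 8.3 points. As an illustration, assume 6 of 12 would respond if every lesion were measurable. Let k of those responders have, as their only lesion, one in the band that is not followed by spiral CT, and suppose their partial response is not scored. Neither the 6 nor k comes from the documents. The exact 95% limits are the 0.025 quantile of Beta(x, n − x + 1) and the 0.975 quantile of Beta(x + 1, n − x).

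| k | Kept in denominator | Exact 95% CI | Dropped from denominator |
|---|---|---|---|
| 0 | 6/12 = 50.0% | 21.1 to 78.9% | – |
| 1 | 5/12 = 41.7% | 15.2 to 72.3% | 5/11 = 45.5% |
| 2 | 4/12 = 33.3% | 9.9 to 65.1% | 4/10 = 40.0% |
| 3 | 3/12 = 25.0% | 5.5 to 57.2% | 3/9 = 33.3% |

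Section 5.5.1 points to the kept column. Each row is the worst case for its k, because every affected subject is taken to be a would-be partial responder.

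**The case against.** **The limits follow from technique.** Each is twice a slice thickness in section 9.3, so they are not arbitrary. That explains where they may come from. It does not justify them here, because section 9.3 limits those settings to other body regions.

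**Consistency is already protected.** Section 8.1.18 asks for the screening study to be repeated, and section 9.3 adds: "When possible, the same method of assessment and the same technique should be used to characterize each identified and reported lesion". This stands within a subject, where a change of scanner would most directly corrupt a response call. It does not make baseline classification comparable between subjects. A subject imaged by both spiral CT and MR might qualify through the CT limit, but the protocol does not say which scan decides.

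**Section 9.3 does not really contradict section 9.1.** A reader might infer a conflict because a 10 mm skin nodule is measurable and a 20 mm mass on MRI is not, although section 9.3 prefers imaging. The documents do not support that reading. The preference applies when both methods have been used to judge antitumour effect; it does not govern measurability. A separate limit for superficial lesions is not a contradiction in itself.

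**Nodes on MR are not wholly without a rule.** A reader might infer that they are. Section 9.2 classes nodes of 10 to under 15 mm short axis as non-measurable with no modality limit; only the positive 15 mm rule is tied to CT. What remains is narrower: that rule does not mention MR, and a palpable node of at least 10 mm diameter can be measurable under 9.3 while its short axis makes it non-measurable under 9.2.

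**Conclusion.** The point holds for non-nodal lesions above 10 and up to 20 mm, and not for lesions in general. For these, the text makes measurability depend on the scanner, lets the scanner vary between subjects, and keeps subjects with only non-measurable disease in the efficacy set.

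Two stronger conclusions are tempting. A reader might infer that the protocol bars a partial response in non-measurable disease. It does not say so: it names RECIST 1.1 and restates no rule for partial response. The supportable statement is that without a measured lesion no percentage shrinkage is defined, and the protocol gives no substitute.

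A reader might also infer a definite understatement of ORR. With 3 affected subjects and a 50% response rate, the expected loss would be 3 × 0.5/12 = 12.5 points. Both inputs are assumptions, and the result is an upper bound because it treats every response in these subjects as partial. For a subject to be affected, the lesion must be in the band, followed without spiral CT, and unaccompanied by another measurable lesion, and the response must be partial. The count may be zero. Since the scoring of such subjects is unstated, neither the direction nor the size of a net bias is established.

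The firm figure is up to 8.3 points per affected subject at 12 subjects. Severity is minor to moderate: ORR is secondary and descriptive, and at 6/12 its exact interval already runs from 21.1 to 78.9%.

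**What to change.** 1. In sections 9.1 and 9.2, use one non-nodal longest-diameter cut-off of 10 mm, with one inequality sign throughout, for CT, MR and PET-MR at slices of 5 mm or less. Keep 20 mm for x-ray and for thicker-slice scans.
2. Apply the 15 mm short-axis node rule to CT and MR alike, and reconcile it with the palpable-node example in section 9.3.
3. State how subjects with only non-measurable disease enter the ORR numerator and denominator.
4. The Protocol Summary gives accrual as closed on April 18, 2022, so reclassify lesions from the existing scans. If responses have already been read, report ORR under both definitions.

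The cost is protocol wording and a review of baseline scans. Section 9.3 already takes measurements from standard-of-care imaging, so no new scans are needed. The documents do not show that existing MR scans have slices of 5 mm or less; any that do not stay at 20 mm, and some dependence on the scanner would remain. The other downside is slightly more measurement error for 10 to 20 mm lesions on MR.

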9.2 Non-measurable Disease

All other lesions (or sites of disease), including small lesions (longest diameter < 20 mm with conventional techniques or < 10 mm using spiral CT scan or pathological lymph nodes with ≥ 10 to < 15 mm short axis), are considered non-measurable disease. Bone lesions, leptomeningeal disease, ascites, pleural/pericardial effusions, lymphangitis cutis/pulmonis, inflammatory breast disease, abdominal masses (not followed by CT or MRI), and cystic lesions are all non-measurable.

9.3 Guidelines for Evaluation of Measurable Disease

Measurements will be recorded for the study from standard of care scans in the medical records maintained as part of standard clinical care. All measurements should be taken and recorded in metric notation using a ruler or calipers. All baseline evaluations should be performed as closely as possible to the beginning of treatment and never more than 4 weeks before the beginning of the treatment.

Note: Tumor lesions that are situated in a previously irradiated area can be considered measurable only if there is documented growth of the lesion, and at least 8 weeks have elapsed since completion of radiation treatments.

When possible, the same method of assessment and the same technique should be used to characterize each identified and reported lesion at baseline and during follow-up. Imaging-based evaluation is preferred to evaluation by clinical examination when both methods have been used to assess the antitumor effect of a treatment.

Clinical lesions: Clinical lesions will only be considered measurable when they are superficial and ≥ 10 mm diameter (e.g., skin nodules and palpable lymph nodes). In the case of skin lesions, documentation by color photography, including a ruler to estimate the size of the lesion, is recommended.

Chest x-ray: Lesions on chest x-ray are acceptable as measurable lesions when they are clearly defined and surrounded by aerated lung. However, CT is preferable.

Conventional CT and MRI: These techniques should be performed with cuts of 10 mm or less in slice thickness contiguously. Spiral CT should be performed using a 5 mm contiguous reconstruction algorithm. This applies to tumors of the chest, abdomen, and pelvis. Head and neck tumors and those of extremities usually require specific protocols.

Ultrasound: When the primary endpoint of the study is objective response evaluation, US should not be used to measure tumor lesions. It is, however, a possible alternative to clinical measurements of superficial palpable lymph nodes, subcutaneous lesions, and thyroid nodules. Ultrasound might also be useful to confirm the complete disappearance of superficial lesions usually assessed by clinical examination.

Endoscopy, Laparoscopy: The utilization of these techniques for objective tumor evaluation has not yet been fully and widely validated. Their uses in this specific context require sophisticated equipment and a high level of expertise that may only be available in some centers. Therefore, the utilization of such techniques for objective tumor response should be restricted to validation purposes in reference centers. However, such techniques may be useful to confirm complete pathological response when biopsies are obtained.

10 RADIATION SAFETY

10.1 Radiation Safety Monitoring and Release Criteria

UW Hospital has established guidelines/policy regarding the release criteria following administration of radioactive material. All institutional policies will be followed in this study. The guidelines below are recommendations only, and the regulations of the institution will take precedence.

Prior to the initiation of this trial, the Radiation Safety Officer will be contacted to determine the release criteria to be followed for subjects participating in the trial. The institution's Radiation Safety Officer will conduct all appropriate training of research staff.

Sponsor suggested guidelines for monitoring for radioactivity and criteria to use for discharge are:

- Starting one day after the CLR 131 infusion, medical physics/radiation oncology personnel will monitor subject radiation levels at 1 meter from umbilicus.
- Subjects will be discharged from the hospital when their radiation level is < 7 mrem/hr and the discharge is cleared by radiation safety personnel.

10.2 Subject Radiation Precautions

Prior to the initiation of this trial, the Radiation Safety Officer will be contacted to determine all required precautions to be followed by subjects participating in the trial. The Radiation Safety Officer will perform all appropriate training of research staff.

Written instructions, approved by the institution's Radiation Safety Officer, describing methods to limit radiation dose to others must be given to the subject prior to CLR 131 infusion. The following precautions, conservatively derived from recommendations of the Society of Nuclear Medicine and Molecular Imaging (Silberstein *et al.*, 2012) and the American Thyroid Association Taskforce on Radioiodine Safety, 2011, are suggested for subjects following the administration of CLR 131 to lessen the risk to others:

For three weeks after each dose of CLR 131:

- Sleep alone and abstain from intercourse
- Do not sleep with infants, small children or pregnant women for three weeks after CLR 131 infusion

For one week after each dose of CLR 131:

- Avoid participating in feeding, clothes changing and similar care of infants and small children
- Limit time with and maintain a distance of approximately 3-6 feet from pregnant women and children
- Do not prepare food for others that requires prolonged handling with bare hands

- Do not share dishes, utensils, towels or face cloths with others prior to washing
- Do not share razors, toothbrushes, food or drinks with others
- Flush toilet twice after use and wash hands for 20 seconds afterwards. Men should urinate sitting down.
- Rinse the sink and wash hands thoroughly after brushing teeth
- Do not stay in a location other than a private residence (such as a hotel)
- Limit the time spent in public places to 1-2 hours if you can maintain 3 feet distance from others and avoid places such as theaters, sports arenas or stadiums, and so forth, where the option of getting a seat farther away from others may not always be possible
- Bathe/shower daily for at least three days after CLR 131 infusion
- Avoid prolonged use of public transportation the first day after CLR 131 infusion

11 ASSESSMENT OF SAFETY

11.1 Specification of Safety Parameters

The Investigator should elicit information regarding the occurrence of AEs through open-ended questioning of the subject, physical examination, and review of laboratory results. Adverse event data collection and reporting, which are required as part of every clinical trial, are done to ensure the safety of subjects enrolled in the studies as well as those who will enroll in future studies using similar agents. Adverse events are reported in a routine manner at scheduled times during a trial. Additionally, certain adverse events must be reported in an expedited manner to allow for optimal monitoring of patient safety and care. The first step is to identify the event using the Common Terminology Criteria for Adverse Events (CTCAE). The CTCAE document provides descriptive terminology for adverse event reporting. A grading (severity) scale is provided for each adverse event term.

All AEs, whether serious or not, will be described in the source documents and the AE page of the Case Report Form (CRF). All new events, as well as those that worsen in intensity or frequency relative to baseline, that occur after administration of study drug through the period of protocol-specified follow-up must be captured.

Specific anticipated adverse events are described in section 2.3.

Information to be reported in the description of each AE includes but is not limited to:

- Medical diagnosis of the event. (If a medical diagnosis cannot be determined, a description of each sign or symptom characterizing the event should be recorded.)
- The date of onset of the event
- The date of resolution of the event
- Whether the event is serious or not
- Action taken
- Outcome
- Relatedness to the study drug (see below)
- Subject's condition is intermittent or continuing
- The grade of the event based on the CTCAE v5.0

11.1.1 *Unanticipated Problems*

The Office for Human Research Protections (OHRP) considers unanticipated problems involving risks to subjects or others to include, in general, any incident, experience, or outcome that meets **all** of the following criteria:

- unexpected in terms of nature, severity, or frequency given (a) the research procedures that are described in the protocol-related documents, such as the IRB-approved research protocol and informed consent document; and (b) the characteristics of the subject population being studied;
- related or possibly related to participation in the research (“possibly related” means there is a reasonable possibility that the incident, experience, or outcome may have been caused by the procedures involved in the research); and
- suggests that the research places subjects or others at a greater risk of harm (including physical, psychological, economic, or social harm) than was previously known or recognized.

11.1.2 *Adverse Events*

An adverse event is any untoward or unfavorable medical occurrence in a human subject, including any abnormal sign (for example, abnormal physical exam or laboratory finding), symptom, or disease, temporally associated with the subject’s participation in the research, whether or not considered related to the subject’s participation in the research.

11.1.3 *Serious Adverse Events (SAE)*

A serious adverse event is defined as any adverse event that meets one of the following criteria:

- Results in death; OR
- Is life-threatening; OR
- Requires hospitalization or prolongs existing hospitalization; OR
- Results in significant or persistent disability or incapacity; OR
- Results in a congenital anomaly/birth defect

Planned hospitalizations for disease-related surgery, routine procedures, non-disease-related procedures, and inpatient hospitalization for radiation protection/exposure levels are not considered SAEs.

